4.1 Inclusion Criteria

Participants must meet all of the following inclusion criteria:

- 18-60 years of age
- Low back pain that has been ongoing for at least half the days in the last 6 months
- Average pain intensity of 3 or higher over the past week on a 0-10 Numerical Rating Scale
- Disability >4 on Roland and Morris Disability Questionnaire
- Tampa Scale for Kinesiophobia score >36
- Has sought care or consultation from a health care provider for back pain
- Meets category < 4 on the Classification System of the Quebec Task Force on Spinal Disorders,⁴⁹ which reflects low back pain without neurological signs
- Working proficiency in English

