This project is a Phase II RCT in which CLBP participants will be randomly assigned to one of two intervention arms. Those assigned to the experimental group will play immersive games that will encourage progressively larger lumbar flexion excursions at each game level and across treatment sessions. Those in the control group will play the same immersive games, but the parameters of the game will require smaller excursions of lumbar flexion to successfully complete gameplay. Treatment frequency and duration is based on existing evidence that graded activity and graded exposure interventions, typically lasting 6-12 weeks with 8-18 treatments sessions, result in significant reductions in disability.^{44,43} Accordingly, participants in this study will complete 18 visits over 9 weeks with the number of sessions tapered across weeks (i.e., 3 sessions/week in weeks 1-3, 2 sessions/week in weeks 4-6, and 1 session/week in weeks 7-9). Our co-primary outcome variables will be change in pain and change in disability from baseline to 1-week post-treatment (Aim 1). We will also examine changes in expectations of pain/harm and lumbar flexion as potential mechanisms of change in pain and disability (Aim 2). Aim 3 will examine maintenance of treatment gains at 1-, 6-, 12-, 24-, and 48-weeks post-treatment.

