9.6 Data Analyses

We will analyze all outcome variables (pain, disability, pain/harm expectancy, and lumbar flexion) using linear mixed-effects (LME) models with treatment (Experimental, Control) as a between-subject fixed effect and time (pre-treatment, 1, 6, 12, 24, and 48 weeks) as a within-subject fixed effect. Given the expected findings, both linear and quadratic time effects will be tested in every model. We will also include demographic covariates (e.g., age, BMI) and potential confounders (e.g., radiating versus non radiating pain) as well as sex stratification in the LME models. Any variables that differ at baseline will be included in the statistical models as potential confounders.

Intention-to-treat analyses are commonly conducted to analyze randomized clinical trial data in the presence of missing values. While various imputation strategies have been proposed to estimate missing data, such as last observation carried forward, use of LME models to analyze longitudinal data renders these strategies largely unnecessary. We will also conduct equivalent per-protocol analyses that will include only successfully adhered participants (i.e., attending $\geq 70\%$ of gaming sessions).

Aim 1. Examine immediate clinical outcomes as a function of treatment. Relative to

the control group, participants in the experimental group will show greater reductions in pain and disability at post-treatment relative to pre-treatment baseline (Hypothesis 1).

To test Hypothesis 1, we will examine the Treatment by Time (baseline-post treatment) interaction in a LME model: a greater reduction in pain and disability in the experimental group than in the control group.

Aim 2. Examine potential mechanisms of pre- to post-treatment changes in clinical outcomes. Participants in the experimental group will exhibit greater pre- to post-treatment decreases in pain/harm expectancy and increases in lumbar flexion as compared to the control group (Hypothesis 2.1). Decreases in pain/harm expectancy and increases in lumbar flexion will be positively related to pre- to post-treatment reductions in pain and disability (Hypothesis 2.2).

Aim 3. Examine maintenance of treatment gains at 1-, 6-, 12-, 24-, and 48-weeks post-treatment. Relative to the control group, participants in the experimental group will continue to show lower levels of pain and disability at each time point as well as increased activity in their natural environment (Hypothesis 3).

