To address aims 2 & 3 we will build and test linear mixed-effects models for each of the outcome variables. For hypotheses 2.1 and 3, pain, disability, pain/harm expectancy, and lumbar flexion will be the outcome variables, while time (linear and quadratic), treatment group, and the interactions of time and treatment group will be the primary predictor variables. For hypothesis 2.2, pain/harm expectancy and lumbar flexion will serve as the outcome variables, while time (linear and quadratic), treatment group, the time-by-group interactions, pain, and disability will be predictor variables. For hypothesis 3, planned comparisons will be conducted to compare the control and experimental groups at each time period for pain, disability, and activity levels in the natural environment. As noted above, covariates will be added to analyses as needed. The significance level for every omnibus test will be set to 0.05, while Holms procedure will be used to control familywise type-I error rate for post-tests at .05.

Checking Assumptions: Assumptions of LME models will be checked by conducting analyses of model residuals. Violations of normality will be addressed by transforming the data, while outliers or influential cases will be handled by conducting sensitivity analyses. In contrast to the standard repeated measures analyses of variance, with their rigid assumptions about the error covariance structure, LME models permit numerous alternative error covariance structures. This allows for modeling of data that exhibit both heteroscedasticity and autocorrelation, which is likely to characterize the data collected for this study.

Additional Analyses: We will use the same analytic framework to analyze additional measures of core outcome domains, including emotional functioning (e.g., CES-D, POMS-2, PROMIS measures), pain vulnerability (TSK, PCS), pain resilience (PRS, PSEQ), and patient global impression of change (PGIC).

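### Section 9.6 lets an unspecified residual check move the co-primary pain and RMDQ analyses to a transformed scale, which changes the quantity tested and can change whether it is significant

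*Combined protocol and SAP*

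**What the plan says.** Section 9.6 sets one framework for everything: "We will analyze all outcome variables (pain, disability, pain/harm expectancy, and lumbar flexion) using linear mixed-effects (LME) models". For Hypothesis 1, "we will examine the Treatment by Time (baseline-post treatment) interaction in a LME model", and the expected finding is "a greater reduction in pain and disability in the experimental group than in the control group".

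Under the heading on checking assumptions, Section 9.6 says "Assumptions of LME models will be checked by conducting analyses of model residuals" and then "Violations of normality will be addressed by transforming the data". The same sentence sends outliers and influential cases to sensitivity analyses. Non-normality is therefore the one finding there that alters the analysis itself. Pain and disability are not exempted.

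The section does not state which residuals are meant (marginal or conditional), by what test or cut-off they fail, which transformation follows, what happens to scores of zero, or on which scale the effect is reported.

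Two other places matter. Section 6.2 describes an 11-point pain scale and an RMDQ of 24 yes/no items, so both outcomes are bounded whole numbers. Section 4.1 requires average pain of at least 3 and "Disability >4 on Roland and Morris Disability Questionnaire", whereas follow-up scores can fall to 0.

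**The concern.** With complete data, the baseline-to-1-week interaction on the original scale is the difference between arms in mean change. On a log scale it becomes a ratio-type effect. On a square-root scale it has no direct reading in the units of the questionnaire. The three tests address different null hypotheses, and under the rule the residuals of the primary model decide which one becomes primary.

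At stake are what the co-primary result means and, in some settings, whether it is significant. A log also needs an added constant once any follow-up score is 0, which is a further open choice. If the untransformed test already behaves well at this sample size, the rule brings these costs without a matching benefit.

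**Working it through.** The plan attaches no figure to this rule, so there is none to reproduce. The check uses its planning values and simulation.

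**1. Is non-normality plausible?** Section 9.2 sets the SD at 75% of the mean and draws from a normal distribution. The share of a normal baseline below zero is Φ(−1/0.75) = Φ(−1.33) = 9%. After a 30% fall with the SD unchanged it is Φ(−0.70/0.75) = Φ(−0.93) = 17.5%. Bounded scores cannot follow that model. The rule looks at residuals, however, not raw scores (step 4).

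**2. Does the scale change the quantity?** Take an assumed baseline RMDQ of 11 for everyone. In arm A all fall 20%, to 8.8. In arm B a fifth fall to 0 and the rest stay at 11, so the mean is 0.8 × 11 = 8.8.
- Raw: 8.8 − 8.8 = 0.
- Square root: 0.8 × √11 − √8.8 = 2.653 − 2.966 = −0.313.
- log(1+y): 0.8 × ln 12 − ln 9.8 = 1.988 − 2.282 = −0.294.

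There is no difference in mean change, but a clear one on either transformed scale.

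Baseline imbalance can have a similar effect. With means 12 to 8.5 (experimental) and 10 to 7 (control), the difference in change is −3.5 − (−3.0) = −0.5, favouring experimental. On the log of the means it is ln(8.5/12) − ln(7/10) = −0.345 + 0.357 = +0.012, favouring control.

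**3. What happens to the test?** Inputs from the plan: 30% and 10% reductions, alpha 0.05, and 209 participants. Assumptions: 1:1 allocation (209/2 ≈ 104 per arm), a two-sided test, and a rounded gamma RMDQ baseline truncated to 5-24 (mean about 11, SD about 4, pre-post correlation about 0.75). The follow-up score is a proportional reduction plus N(0, 3.3) noise, rounded and clipped to 0-24. The test is Welch on change, which is the complete-data interaction contrast. There were 1,500 to 2,500 trials per scenario, and ranges are over repeated runs. At 2,000 trials the Monte Carlo standard error near 5% is √(0.05 × 0.95/2000) = 0.5 percentage points.

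| Scenario | Raw significant | log(1+y) significant | Raw and log disagree |
|---|---|---|---|
| 10% vs 10% (no effect) | 4-6% | about 5-6% | – |
| 20% vs 10% | 63-66% | 45-48% | about 22% |
| 30% vs 10% (planned) | 99.5% | 94.9% | about 3-5% |
| Equal mean change, 20% full recovery vs uniform 20% | about 5% | about 60% | – |

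The 30% vs 10% rejection rates come from one run. Square root lies between raw and log: 56-57% power at 20% vs 10%, and 37-42% rejection in the last row. With no effect, the chance that at least one of the three scales is significant was 7.7%.

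A second design used 105 per arm, six time points, a normal latent variable with r = 0.7 and 1,000 trials per scenario, and it included pain (assumed mean 5.5). Raw and log disagreed in 0-8.5% of trials at 30% vs 10%. At 20% vs 10% they disagreed in 11% (pain) and 18% (RMDQ).

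**4. How often would the rule act?** Shapiro-Wilk at p < 0.05:
- Marginal residuals: 98-100% in the first design, 86-100% in the second at 30% vs 10%.
- Conditional or change-score residuals, uniform response: 5-31% in the first design. In the second, conditional residuals at 30% vs 10% gave 9-26%.
- Absolute skewness above 0.5, second design at 30% vs 10%: 0%.
- Equal-mean mixture of step 3: 100% on marginal and 99% on change-score residuals.

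The answer runs from never to always, depending on choices the plan leaves open. In the mixture, where the scale matters most, both residual types set it off.

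**The case against.** Several points on the other side are sound.

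- A reader might infer that the rule is bound to act on the co-primaries. The documents do not support this: they fix neither residual type nor criterion, and on conditional or change-score residuals a formal test usually passes under uniform response.
- A reader might infer that transforming would reverse the conclusion. At the planned 30% versus 10%, estimates on the two scales had opposite signs in at most 0.1% of trials. No simulated trial in any scenario was significant in opposite directions. The realistic risk is a change in significance.
- A reader might infer that the plan commits itself to a difference in points. It does not. Section 9.2 works in percentage decreases and gives no important difference in points, and proportional effects are arguably closer to a log scale.
- The equal-mean mixture is constructed. Nothing in the documents predicts it, and the arms' distributions do differ there, so the log rejections are not false positives for a distributional difference.
- Under uniform response, transforming keeps the error rate near 5% and loses power, so it does not favour the intervention.
- Sections 5.2, 6.2.3 and 9.2 keep the statistician blinded to the end of the study.
- The simulated SD, about 37% of the mean, is not the plan's 75%. The baseline floor is also softer than assumed, because entry is judged at Visit 0 and RMDQ is repeated at Visit 1.

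Blinding limits choosing a scale for its result. It does not keep the quantity fixed, because residuals can move a blinded statistician to another scale. Naming the check and the transformation would remove the discretion, but the primary quantity would still depend on the data.

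**Conclusion.** The point holds as an improvement the plan should make. Section 9.6 contains a rule, not just a gap: it reaches both co-primaries, depends on the data, is unspecified, and changes what is estimated.

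Its practical size depends on the true effect. At the planned effect it is small, with 3-5% of trials changing significance between raw and log. At 20% versus 10% it is material: about 22% change, and power falls by some 18 percentage points (63 − 45, or 66 − 48). If response shapes differ between arms the scales can diverge sharply, but the 5% against 60% figure is only an illustration of that.

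The untransformed test kept its level at 4-6% with about 104 per arm, so protecting the error rate does not require the rule. These figures rest on assumed baseline distributions, 1:1 allocation, a two-sided test and complete data; the first design covers RMDQ only. The text finding and the dependence on scale need none of these assumptions.

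**What to change.** In Section 9.6, exempt pain and disability from the transformation rule. State that the mixed model on the original scale remains the primary analysis whatever the residual checks show, with robust (sandwich) standard errors or a bootstrap interval if residuals are non-normal.

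Allow a transformed analysis of these outcomes only as a labelled sensitivity analysis, with the transformation, the handling of zeros and the reporting scale named in advance.

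The cost is about a sentence of SAP text and possibly slightly wider intervals. Data collection and sample size are unaffected.

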10. DATA COLLECTION AND QUALITY ASSURANCE

10.1 Data Collection Forms

All data collection forms are paper-based or electronic (eCRF) with the exception of

the prescreen survey which is always an online form, but can be completed by study staff as a source document during a phone interview. As source documents, all forms are signed or electronically verified and dated by a study staff member. Forms are identified with Participant Identification Numbers with no personal identifying information. The Study Coordinator or Research Assistant transfers all data from the paper forms to the database. Every 2-weeks a Research Assistant performs a quality assurance check by comparing paper-based forms to data entry in the database.

All paper data collection forms will be kept in a locked file cabinet in the Study Coordinator's office or the respective offices or laboratories of the PIs. Data will also be entered into an electronic database. The data management system has been developed by the Virginia Commonwealth University Office of Research and Sponsored Programs. Specifically, we will use REDCap™, a web application for building and managing online surveys and databases. Subjects will be identified by a unique identification number and no personal identifying information will be stored in the study database or used in any of the analyses files.

10.2 Data Management

This is a single site study and as such Virginia Commonwealth University will serve as the Coordinating Center and is responsible for all data management.

10.3 Quality Assurance

10.3.1 Training

Prior to data collection, the following will take place:

1. The Steering Committee will review and approve all protocols.
2. All study personnel will be trained in all study procedures for which they are responsible.

10.3.2 Quality Control Committee

This is a single site study and the Steering Committee will be responsible for overseeing quality control.

10.3.3 Metrics

The PIs will monitor treatment administration records on a monthly basis to determine whether study participants are receiving appropriate treatments as prescribed.

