Our co-primary outcome variables will be change in pain and change in disability from baseline to 1-week post-treatment (Aim 1). We will also examine changes in expectations of pain/harm and lumbar flexion as potential mechanisms of change in pain and disability (Aim 2). Aim 3 will examine maintenance of treatment gains at 1-, 6-, 12-, 24-, and 48-weeks post-treatment, additional measures of emotional functioning, pain vulnerability, and pain resilience, and real-world activity monitoring

[figure not shown]
(See Recruitment and Pre-Screening – Figure1).

Figure 1

Study Title

VIGOR - Virtual Immersive Gaming to Optimize Recovery in Low Back Pain

Objectives

The co-primary clinical outcomes are changes in pain and disability. Secondary objectives are to examine potential mechanisms of pre- to post-treatment changes in clinical outcomes and maintenance of treatment gains.

Design and Outcomes

VIGOR is a Phase II, double-blind, randomized, placebo-controlled trial to test the efficacy and safety of a novel, immersive, virtual reality intervention on outcomes of pain, disability, pain/harm expectancy, and lumbar flexion in individuals aged 18-60 years of age with chronic low back pain.

Individuals with chronic low back pain will be randomly assigned to play one of two versions of the virtual reality game suite for 9-weeks. In the experimental group, gameplay will promote progressive increases in lumbar flexion. The control group will play the same immersive video games, but the parameters will be modified such that

only small excursions of lumbar flexion are needed to successfully complete gameplay. The co-primary clinical outcomes of changes in pain and disability will be assessed at 1-, 6-, 12-, 24-, and 48-weeks post-treatment. Additionally, individual differences in expected pain, expected harm, and lumbar flexion will be measured at pre-treatment baseline and at each of the follow-up intervals in the laboratory. Finally, participant activity in their natural environment will be monitored for 7 days following each follow-up laboratory visit using accelerometry.

Interventions and Duration

Participants will complete 18 intervention visits over 9 weeks with the number of sessions tapered across weeks (i.e., 3 sessions/week in weeks 1-3, 2 sessions/week in weeks 4-6, and 1 session/week in weeks 7-9).

Sample Size and Population

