5.2 Handling of Study Interventions

The principal investigators, the statistician, and members of the data collection team will remain blinded to intervention assignment throughout the duration of the study. They will be given the identifying codes only at the end of the study when it is necessary to interpret the results. The un-blinded study coordinator, who is responsible for scheduling testing and treatment sessions, will greet participants and escort them to the testing lab; however, the study coordinator will not participate in the assessments of clinical outcomes or testing.

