6.2.2 Enrollment, Baseline, and/or Randomization (Visit 1)

Enrollment

A single informed consent form that describes both screening and study procedures will be used. The date of enrollment in The VIGOR Study will be defined as the date all of the screening criteria are met and the individual agrees to participate. The enrollment date will be recorded on a case report form along with the allowable window between screening and randomization.

- CRF: Randomization and Enrollment Form

Baseline Assessments

Participants enrolled in the study will complete the following baseline assessments at Visit 1:

- Numeric Pain Rating Scales 7-day & 24-hour
- Roland-Morris Disability Questionnaire
- Medication Log
- Adverse Events Log
- Numeric Pain Rating Scale – Right Now
- Standardized Reaching Paradigm (Pain & Harm Expectancy, Lumbar Spine Flexion)
- Tampa Scale for Kinesiophobia
- Center for Epidemiologic Studies – Depression
- Pain Catastrophizing Scale
- Pain Resilience Scale
- Pain Self Efficacy Questionnaire
- Brief Pain Inventory – Short Form
- PROMIS-Anxiety
- PROMIS-Depression
- PROMIS-Positive Affect
- PROMIS-Meaning and Purpose Scale
- Life Fulfillment Scale
- Profile of Mood States
- Real World Activity Monitoring
- Treatment Evaluation Inventory – Short Form

Randomization

The study coordinator will use a sex-stratified random allocation table, created by the study statistician, to assign participants to a treatment group. A maximum of 7-days will be permitted between enrollment and randomization or initiation of the study intervention.

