6.2.3 Blinding

The principal investigators, the statistician, and members of the data collection team will remain blinded to intervention assignment throughout the duration of the study. They will be given the identifying codes only at the end of the study when it is necessary to interpret the results. The un-blinded study coordinator, who is responsible for scheduling testing and treatment sessions, will greet participants and

escort them to the testing lab; however, the study coordinator will not participate in the assessments of clinical outcomes or testing.

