6.2.6 Reasons for Early Termination

A subject would be discontinued from the study intervention if a medical condition develops that precludes the continuation of the treatment intervention. For participants who discontinue The VIGOR Study prior to completing all scheduled treatment sessions (regardless of the reason), we will make every attempt to obtain the outcome measurements. If the study participant is unwilling or unable to undergo the laboratory-based tests (e.g., difficulty tolerating the protocol, experienced an adverse event to a lab test) we will still attempt to obtain the clinical outcome

measures. In instances where an adverse event does occur, we will follow-up with participants until the event is resolved or until the IRB deems it unnecessary to continue to follow the participant.

If the participant complains of any sudden onset of muscle or joint pain, the current session will be terminated, and the Principal Investigator will be contacted to complete an assessment. If he is unavailable, one of the other clinicians on the study team will be contacted to provide a clinical assessment of the participant. They will then consult with the PI to assess if the participant should continue to stay on protocol. If an exclusion criterion is identified from the presenting signs and symptoms, the participant will then be withdrawn from the study. If the presenting signs and symptoms do not meet the exclusion criteria, the participant will be invited to return for their next scheduled visit when the sudden onset of symptoms has abated. Upon return, the PI or a clinician on the study team will again assess the participant and make a clinical judgement about their fitness to continue with the intervention. However, if the participant has a second episode of sudden onset of joint or muscle pain, they will be immediately withdrawn from the study.

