minimizes potential risks to the participant in that they do not require any lifting; thus, spine loads are minimal. We further minimize risk by informing the participants that they are free to stop at any time if they find the procedure too uncomfortable. Finally, each session will begin with the participant starting with the most basic movement task to encourage success and to allow for the adaption of movement patterns while reducing the risk of exacerbating back pain symptoms.

Some participants could feel nauseated from being in the virtual reality environment, but this is minimized by having precise synchronization of motion of the headset and the graphics presented to the participant. Care is also taken to avoid rapid changes in the visual scenes that can induce motion sickness. Finally, we are pre-screening our applicants to ensure they are not highly susceptible to motion sickness.

There is a risk of falling as vision of the real world is fully occluded by the virtual reality headset. Risk of falling is minimized by having the participant first stand in the testing area and then put on the headset. None of the virtual reality activities require steps to be taken; in fact, we will instruct participants to move their feet as little as possible. Further, the headset will be removed while the participant is still in the testing environment; hence, at no time will participants be ambulatory while their real world vision is obstructed. Additionally, the testing area is an open space with a level surface, minimizing the risk of injury if a participant should fall. Two research staff members will conduct every appointment which allows one to run the software and the other to monitor the study subject.

In keeping with Virginia Commonwealth University Institutional Review Board and US Department of Health and Human Services, Office for Human Research Protections requirements, all study personnel who interact with participants or have access to research data will maintain valid certification of training in the protection of human research participants.

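### The plan declares the PIs, statistician and data collection team blinded throughout, but gives them, or staff who are probably among them, tasks that can reveal the arm and states no safeguard

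*Combined protocol and SAP*

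**What the plan says.** The Précis (Design and Outcomes) describes the trial thus: "VIGOR is a Phase II, double-blind, randomized, placebo-controlled trial to test the efficacy and safety". Section 6.2.3 names the blinded roles: "The principal investigators, the statistician, and members of the data collection team will remain blinded to intervention assignment throughout the duration of the study". It adds: "They will be given the identifying codes only at the end of the study when it is necessary to interpret the results". Sections 5.2 and 9.2 repeat both statements. The only role named as un-blinded is the study coordinator, whose part is limited in section 5.2: "however, the study coordinator will not participate in the assessments of clinical outcomes or testing".

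The same document assigns these tasks:

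- PIs, section 10.3.3: "The PIs will monitor treatment administration records on a monthly basis to determine whether study participants are receiving appropriate treatments as prescribed".
- Statistician, section 6.2.2: participants are assigned from a "sex-stratified random allocation table, created by the study statistician". Section 9.2 confirms that the statistician does the block randomization.
- Session staff, section 7 (Virtual Reality Game Play): "Two research staff members will conduct every appointment which allows one to run the software and the other to monitor the study subject".
- PIs again, section 6.2.6: after sudden muscle or joint pain in a session, "the Principal Investigator will be contacted to complete an assessment".

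Two masking safeguards are stated. The coordinator prepares masked adverse event reports for the PIs (section 7.2), and the Medical Safety Committee works from masked data (section 12).

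**The concern.** A promise that a role stays blinded holds only if that role's tasks can be done without knowing the arm, or if a procedure hides the arm. Here the PIs check treatment delivery, the statistician writes the sequence, and session staff watch participants play. For none of these does the plan say how the arm stays hidden.

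Three kinds of judgement are at stake. The PIs and co-investigators classify adverse events, with an event form that rates relationship to the intervention (sections 6.2 and 7.3), and the PI helps judge fitness to continue (section 6.2.6). Section 9 leaves choices until data are in hand: the missingness verdict that selects the imputation method (9.3), and covariates, transformations and handling of outliers (9.6). Staff instruct and run the reaching test that yields lumbar flexion. If the arm is known, each can drift, and the trial report could not document the blinding that it claims.

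**Working it through.** No arithmetic applies. The check sets each role's tasks against what would reveal the arm.

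1. **What separates the arms.** Both arms have the same visits and games. Under section 5.1, experimental targets call for 15, 30, 45 and 60 degrees of lumbar motion, and the gain falls from 1 to 0.85 by week 4; control targets need only 15 degrees. Attendance or game version alone therefore shows nothing. Target or gain settings show the arm, and how far a participant bends may suggest it.

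2. **PIs.** Section 10.3.3 does not describe the records. If they hold settings, checking them against the prescription reveals the arm. If they hold only attendance and game version, it does not. The second reading is possible but would largely duplicate section 5.4, where the coordinator already tracks attendance and a committee including the PIs reviews it. Where masking is intended the plan says so (sections 7.2 and 12); section 10.3.3 does not. Any exposure starts at the first monthly check.

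3. **Statistician.** The person who generates the sequence is also listed as blinded. Both can be true if the table carries neutral codes and someone else holds the key. Releasing codes at the end (section 6.2.3) implies this, but no section describes the coding or names a key holder. Any exposure predates enrolment.

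4. **Session staff.** One of the two runs the software and the other watches. Section 6.2.4 places pain ratings, the adverse event log and the reaching task in the treatment visits (2-19), and section 9.5.2 takes secondary outcomes at nine of those 18 visits (2, 5, 8, 11, 13, 15, 17, 18 and 19). The coordinator is excluded from testing, and no one else is routinely placed at these appointments. So session staff very probably collect these data, which would make them part of the data collection team. That is an inference; no section says it. Nor does any section separate them from whoever runs Visits 20-24. Any exposure starts at Visit 2.

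5. **Roster.** The Study Team Roster lists the un-blinded coordinator under a heading that joins coordination with data collection, while the data collection team is declared blinded. This too needs reconciling.

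6. **Outcomes reached.** Pain and RMDQ disability are self-reported (section 6.2), and neither the PIs nor the statistician is said to collect them. Adverse event classification, continuation decisions, post-data analysis choices and reaching tests are closer to the roles concerned.

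**The case against.** The strongest reply is that every conflict rests on something the text leaves open. The PIs' records may contain no settings. The code-release wording points to coded arms. The operator may load a settings file without seeing the arm, and section 7 speaks of research staff, not of the data collection team. Section 12 mentions manuals of operations, which may supply the detail. Lumbar flexion is measured by motion capture on a task well inside the range of motion, with an instruction to move naturally, so staff influence on it should be modest.

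Most of this stands, and it limits the conclusion. A reader might infer that blinding is shown to fail, including for adverse event assessment. The documents do not support that. Section 7.2 gives the PIs masked adverse event reports, section 12 gives the Medical Safety Committee masked data, and the coordinator's own adverse event assessment is openly un-blinded, so no blinding is claimed there. A reader might also infer that the co-primary results are compromised; their self-reported nature argues against this.

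What the reply does not remove is the absence of any stated procedure. A masked report is only a partial safeguard for a PI who could learn the arm from treatment records, and hiding a settings file does not stop a monitor from seeing how far a participant bends.

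**Conclusion.** The whole-trial blinding stated for these three groups is not secured by the tasks the plan assigns. For the PIs, sections 10.3.3 and 6.2.3 are unreconciled on their plain wording. For the statistician, the gap is undocumented coding and an unnamed key holder. For session staff, exposure is likely but rests on the inference that they collect the data.

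All 230 participants could be affected. Exposure lies mainly in PI judgements on adverse events and continuation (partly mitigated by the masking in sections 7.2 and 12), analysis choices made after data are seen, if the statistician makes them, and staff-run reaching tests. The co-primary outcomes are least exposed. The size and direction of any bias cannot be derived from the documents, and no sample size or power figure changes. The change should be made because it is cheap and protects a property the trial claims.

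**What to change.** - **Section 10.3.3.** The already un-blinded coordinator checks game settings against assignment and gives the PIs only arm-free summaries of attendance and delivery. Cost: the person who assigns the arms also checks them, so that check is not independent, and the PIs lose direct sight of settings.
- **Sections 6.2.2 and 9.2.** The statistician issues the table with neutral codes. The coordinator sets the code-to-arm link at random and holds the key until database lock. Cost: wording and a short key-holding procedure.
- **Section 6.2.4.** Where existing staffing allows, the operator of a participant's game sessions does not run that participant's reaching test at Visits 20-24. Cost: some planning of the rota. Reaching data collected during treatment visits stay exposed.
- **Section 6.2.3 and the roster.** State whether session staff belong to the blinded data collection team, and reconcile the coordinator's listing.

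Any role for which this is not done should be reported as not blinded. No new staff are needed. There is no need to require that participants complete their scores before meeting any staff; that would clash with the coordinator greeting and escorting them (section 6.2.3).
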